Trauma Informed Guilt Reduction Therapy

NCT02512445

Original Document Date: November 14, 2024

8. Aims and Objectives

Primary Aim: To evaluate the efficacy of TrIGR for reducing deployment-related guilt in Veterans of OEF/OIF/OND.

Hypothesis 1: Veterans in TrIGR compared to Veterans in supportive care therapy (SCT), will have significantly greater reductions in deployment-related guilt severity at the end of treatment and post-treatment follow-up.

Secondary Aims: To examine whether TrIGR reduces distress and shame and improves quality of life. We are also interested in the degree to which gains are maintained during the follow up periods.

Hypothesis 2: Veterans in TrIGR, compared to Veterans in SCT, will have significantly greater reductions in distress, shame, guilt cognitions, avoidant coping, and significantly more improvement in their quality of life at the end of treatment and at post-treatment follow-up.

Hypothesis 3: Per the NAG model, guilt cognitions, distress and avoidant coping will partially mediate the treatment effect on guilt severity.

Exploratory Aim: By including Veterans with a variety of deployment-related presenting problems, we will be able to conduct exploratory analyses that will inform future research regarding for whom and under what conditions TrIGR is most effective.

Objective 1: To explore relationships between TrIGR effects and PTSD and depression symptom severity, suicidal ideation (SI) and alcohol/substance use.

Objective 2: To explore whether reductions in guilt, shame, and avoidant coping will partially mediate the treatment effect on PTSD symptoms among **Veterans with a PTSD diagnosis** and/or depression symptoms among **Veterans with a depressive disorder**.

9. Approach

9.1. Design. This prospective, randomized, controlled trial will assess the efficacy of TrIGR as compared to SCT for the treatment of male and female Veterans with guilt related to a traumatic event that occurred during deployment. 150 participants will be enrolled through the San Diego and Providence VAs and randomized at the individual level. All eligible participants will complete an in-person baseline assessment, receive 6 sessions of TrIGR or SCT in individual format, complete weekly measures related to the primary and secondary aims, and complete a follow-up assessment immediately post-treatment, and 3- and 6-months later.

9.2. Timeline. We propose a study lasting 4 years including:

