In the second stage, we will perform sensitivity analyses for the impact that potentially informative missing data may have on the analyses. The selected method of data analysis is robust with respect to drop-out and missing data, unless the drop-out mechanism or cause of missing is informative. We will use pattern-mixture models to assess if there is bias due to drop out or missing data. These mixed models allow us to assess whether important estimates are dependent on missing data patterns, and provide overall estimates of effects by averaging over the various missing-data patterns [80]. In addition, we will consider the extension of the Pattern-Mixture models [81], which includes the incorporation of random effects in the Pattern mixture model, which allow subject-to-subject heterogeneity. All hypothesis tests will be intent-to-treat, using SPSS version 21, and will be two-sided at the .05 level where applicable. We will adjust p-values for multiple testing within each hypothesis separately by using a Bonferroni correction whenever more than one variable is being tested.

Type I error will be controlled through the following steps. The data analysis method we selected reduces the number of dependent variables drastically. We have restricted potential predictors to those with strong evidence and/or strong rationale for having an effect on the dependent variable, and in most cases we have further restricted potential predictors to one representative of each. Also, an adjusted significance level (.01 rather than .05) will be used if applicable.

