Hypothesis 1: Veterans in TrIGR, compared to Veterans in SCT, will have significantly greater reductions in deployment-related guilt severity (TRGI) at the end of treatment and follow-up period. This hypothesis will be tested using Mixed Effects models. We will examine two specific forms of the Mixed effects model strategy; random regression models (RRM), also known as hierarchical models (HLM), Linear Mixed Effects models (LMEs) or multilevel models; and mixed model analysis of variance (MMANOVA). The Hierarchical Linear Model assumes that change over time is linear while MMANOVA considers time as a categorical classification variable and does not assume any specific profile between the outcome variable and time. Each outcome variable will be graphed versus time for each subject to evaluate what function of time bests describes the data. If the change is linear we will precede with the LMEs structure. If the time pattern is not immediately apparent we will proceed with the MMANOVA. This method allows the inclusion of subjects with missing data or those who were terminated early in the study, without relying on data imputation procedures. A fully saturated treatment by time model will be utilized for inference. Co-variance structure will be chosen based on Akaike's Information Criterion (AIC). Random group level treatment effects will also be evaluated for importance based on the model AIC. Denominator degrees of freedom will be calculated using the Kenward-Roger small sample correction.

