Data will be analyzed from all randomized subjects on whom we have a baseline assessment and at least one post-baseline evaluation. Responses at baseline through 6 months follow-up will be nested within subjects. Slope (change in outcome over time) will be entered into the model as a random factor and interacted with treatment group. Intercept and slope will be modeled as random effects nested within subject, and treatment group will be a fixed effect. If it is needed based on analyses in stage one, baseline covariates (e.g., demographics) will also be entered as fixed effects. Site and the Treatment by Site interaction will be included as “nuisance parameters;” that is, they must be included to account for possible overall site effects (Site) or possible site differences in treatment effects (Treatments X Site). With the balanced design (equal numbers at each site in each group), ignoring these would not increase the probability of Type I error, but it would increase the Error Sum of Squares, thus increasing the probability of Type II Error. The main effect of treatment represents the common effect size across sites if there is one, or the average site effect, if there is heterogeneity across sites. This is true because sample sizes will be balanced across treatment groups and sites. In any case, the analysis procedures will include site and site interaction effects to avoid allowing site effects to bias treatment comparisons. However, if we detect any imbalances between the treatment groups within each site, we will follow the primary analyses above with subsequent analyses considering the imbalances to verify that the conclusions are not affected by the imbalances.

Hypothesis 2: Veterans in TrIGR, compared to Veterans in SCT, will have significantly greater reduction in distress (BSI-18), shame (ISS), and significantly more improved in their quality of life (WHO-QOL-BREF) at the end of treatment and at follow up periods. This hypothesis will be analyzed using a method similar to that for testing hypothesis 1.

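### Hypothesis 1 has no single pre-specified deciding test: the time model is picked from plots of the outcome, and no visit, contrast or any/all rule is primary

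*Combined protocol and SAP*

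**What the plan says.** Section 9.8.1 names one primary variable, TRGI guilt severity. Section 8 states Hypothesis 1 as "significantly greater reductions in deployment-related guilt severity at the end of treatment and post-treatment follow-up". The follow-up assessments are at 3 and 6 months, so three post-baseline visits are in play.

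The Hypothesis 1 text in Section 9.11.2 then says, in order:

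- The shape of change is to be read from plots: "Each outcome variable will be graphed versus time for each subject to evaluate what function of time bests describes the data".
- One branch leads from those plots to the linear mixed model: "If the change is linear we will precede with the LMEs structure".
- The other branch leads to MMANOVA, the plan's term for the model with time as a categorical factor: "If the time pattern is not immediately apparent we will proceed with the MMANOVA".
- A later sentence names a model for the tests, "A fully saturated treatment by time model will be utilized for inference", and leaves the covariance structure to AIC.
- The next paragraph describes a slope model: "Slope (change in outcome over time) will be entered into the model as a random factor and interacted with treatment group". Both the intercept and the slope vary by subject.
- Site and its interaction with treatment enter as nuisance terms. The treatment main effect is also interpreted, as the common or average effect across sites.

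On multiplicity, Section 9.11.1 adjusts "using a Bonferroni correction whenever more than one variable is being tested". It adds that a .01 level replaces .05 where applicable, without saying when that is. Hypothesis 2 is to be analysed by a similar method.

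**The concern.** Three things are left open.

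1. **Time model.** It is chosen by looking at outcome plots. There is no criterion for linearity and no statement that the plots are blind to arm or pooled over arms. A clearly curved pattern has no branch: it is neither linear nor unclear. Section 8's interest in whether gains are maintained makes a curve plausible.
2. **Tested effect.** With four assessments, a saturated treatment-by-time model read strictly gives a 3-df interaction test. Slope by treatment is a 1-df test. The text does not say which governs.
3. **Decision rule.** Hypothesis 1 joins end of treatment and follow-up with 'and'. It names no primary visit or contrast, and does not say whether one or all must be significant. The Bonferroni rule covers variables, not visits.

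Two analysts could each follow the text and report different conclusions on the trial's only primary hypothesis. Hypothesis 2, the mediation analysis and the first exploratory objective reuse the same procedure.

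**Working it through.** **Inputs from the documents.** 150 participants, 1:1, so 75 per arm (9.1, 9.5.2). Two-sided .05 (9.11.1). Difference growing linearly from 0 to 0.5 SD at the last time point, 10% to 20% attrition, correlations 0.2, 0.5 and 0.8 (9.11.2, power paragraph). Four assessments (9.3).

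**Assumptions not in the documents.** Visits at 0, 1.5, 4.5 and 7.5 months; compound symmetry; SD 1; dropout spread evenly. At 20% attrition, 75 × 0.20 / 3 = 5 per arm leave before each post-baseline visit and 60 complete.

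**Formulas.** Let d be the vector of true arm differences at the four visits and C the covariance of its estimate, C = 2(Σ n_p V_p⁻¹)⁻¹, summed over dropout patterns p with n_p participants per arm.

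- Slope: b = (X'C⁻¹X)⁻¹X'C⁻¹d with X = (1, t) if baseline means are free, or X = t if they are constrained equal. Power = Φ(b/SE − 1.96).
- Saturated 3-df test: λ = c'S⁻¹c, where c holds the three differences in change from baseline and S is their covariance. Power = P(χ²₃(λ) > 7.81).
- Conflict rate: 400,000 draws of the difference vector, both tests applied to each.

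**The plan's 90% first.** It cannot be reproduced as one number, because the number of occasions, the covariance and the test behind it are not stated. The free slope at correlation 0.5 and 10% attrition gives 89.2% with these visit times, or 87.5% with equal spacing. At 20% attrition and correlations 0.2 / 0.5 / 0.8 it gives 69 / 86 / 99.8%, or 83 / 96 / 100% if the weekly measures also enter. The figure is reached in some settings and not in others.

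**Numbers at correlation 0.5, 20% attrition.**

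- Linear effect, free slope: b = 0.5/7.5 = 0.0667 per month, SE 0.0218, z = 3.05, Φ(1.09) = 86%.
- Linear effect, 3-df: λ = 9.33, power 73%.
- Early effect held at 0.5 SD, free slope: b = 0.0534, SE 0.0218, z = 2.44, Φ(0.48) = 69%.
- Same effect, 3-df: λ = 13.08, power 87%.
- 6-month difference adjusted for baseline: SE 0.1565, z = 0.5/0.1565 = 3.19, Φ(1.23) = 89%.

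| Power, 20% attrition, correlation 0.2 / 0.5 / 0.8 | Linear effect | Early and held |
|---|---|---|
| Slope, baselines free | 69 / 86 / 99.8% | 50 / 69 / 97% |
| Saturated, 3 df | 52 / 73 / 99% | 67 / 87 / 99.9% |
| Slope, baselines constrained equal | 87 / 93 / 99.9% | 95 / 92 / 99% |
| 6-month difference, baseline-adjusted | 80 / 89 / 99.6% | 80 / 89 / 99.6% |
| Free slope and 3-df verdicts conflict | 21 / 15 / 1% | 28 / 24 / 3% |

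With equal spacing at correlation 0.5, slope against 3-df is 85% against 71% (linear) and 80% against 87% (early and held), so the reversal does not depend on the assumed visit times.

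**Any/all rule.** Under the linear effect the end-of-treatment difference is only 0.5 × 1.5/7.5 = 0.1 SD. If 'and' means that unadjusted change must be significant at both end of treatment and 6 months, power at correlation 0.5 is about 8%. Under the early, held effect it is 72%, against 81% for 6 months alone.

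**The case against.** The strongest defence is that the plan is less open than it looks. The outcome, model family, alpha and analysis population are fixed, and the plots are per subject, not by arm. The saturated-model sentence can be read loosely, as all main effects plus the interaction under whichever time form is chosen. The slope text then describes the linear branch, and nothing contradicts. The power paragraph also leans towards a trend test: its effect is a linear trend, and its first two methods use person-specific regression coefficients and the random regression model.

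Much of this stands. The loose reading is available, so Section 9.11.2 should not be called flatly self-contradictory. But on that reading the plot-based choice decides the test. On the strict reading the 3-df test names no visit or direction, and the slope-by-treatment term is a different tested effect. Neither reading supplies a primary contrast. The power paragraph also reports several methods and does not say which test will be run.

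A reader might infer two stronger points:

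- **That Type I error is inflated.** It stays at 5% if the time shape is judged pooled over arms and one test is then run. It could rise if the arms' curves are viewed separately or any significant result may count. The text neither states nor excludes these.
- **That the 90% power is wrong.** Without the test, occasions and covariance behind it, the documents do not show that.

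The .01 clause probably does not bear on Hypothesis 1, which has one variable. It should still be settled in words.

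**Conclusion.** The concern holds as a gap in the confirmatory specification: the outcome is fixed and the deciding test is not. At correlation 0.5 the two tests that the text supports differ by 13 points of power under the linear effect (86 − 73) and by 18 points the other way under an early, held effect (87 − 69). They conflict in 15% and 24% of trials. At correlation 0.8 conflict is rare (1% and 3%). These sizes rest on the assumed visit times, compound symmetry and even dropout. The finding that no contrast or rule is named rests on the text alone.

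It should be closed before outcomes are seen by arm, since a later choice would not be credible. The documents do not support the inference that only one analysis is right. Several would do if fixed in advance.

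**What to change.** Delete the plot-based choice. Before outcomes are seen by arm, pre-specify one model, one primary contrast and the rule for the other visits. State that Hypothesis 1 is tested at two-sided .05 and that the .01 level does not apply to it. Restate power for the chosen contrast, and use the same model for Hypothesis 2.

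One acceptable choice:

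- Responses at post-treatment, 3 and 6 months; categorical time, treatment and treatment-by-time.
- Baseline guilt severity, gender (the randomisation stratum) and site as covariates; Kenward-Roger as planned.
- The planned Treatment by Site term kept, but centred so that the treatment contrast is the average over the two sites.
- Primary contrast: the adjusted 6-month difference, where the power paragraph places its 0.5 SD. Power is 80 / 89 / 99.6% at 20% attrition and 84 / 92 / 99.8% at 10%.
- Then 3 months and end of treatment in fixed sequence at .05, with the slope model as a sensitivity analysis.

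The cost is SAP wording and a new power statement; no new data are needed. The downsides of this choice are:

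- A slope model with baselines constrained equal has more power at correlations 0.2 and 0.5 under both shapes (87 / 93% linear, 95 / 92% early and held). It is an equally acceptable pre-specified choice.
- End of treatment, reached through the sequence, has about 7% power under the linear effect and 78% under the early, held effect at correlation 0.5.
- With sites of 100 and 50, the centred Treatment by Site term gives about 87% instead of 89%. If the contrast were read at one reference site, even with equal sites, it would be about 74%, so the centring must be written down.

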9.3. Procedures. Eligible Veterans will be recruited from two VA Medical Center sites, one in San Diego, CA, and one in Providence, RI. Potential participants will be receiving or presenting to care at VA enrollment, primary care, mental health, MST, or other VA services and will be referred by clinicians or staff in those clinics (see letters in Support 2e - 2g). Veterans may also self-refer to the study in response to advertising materials that will be distributed in patient areas and in the community. All potential participants will undergo a brief (15 minute) screen (following informed consent to be screened) conducted by the site project coordinator to determine preliminary eligibility. Veterans who meet the screening requirements will complete consenting procedures and will be invited for a full baseline assessment. Participants who meet inclusion/exclusion criteria as confirmed by the baseline assessment will be randomized to TrIGR or SCT. All participants will be assessed at baseline, immediately post-treatment, and at 3- and 6-month post-treatment follow-ups. Participants will be compensated for completing each of the four assessments with \$40 per assessment. We anticipate that baseline assessments will take approximately 3 hours and follow-ups will take approximately 2 hours. Participants will also complete brief weekly self-report assessments (15 minutes) during treatment. We will attempt to obtain follow-up data on all participants, regardless of whether they complete the intervention.

9.4. Participants: Inclusion/Exclusion Criteria, and Rationale. Participants will be male and female OEF/OIF/OND Veterans, at least 18 years of age, who endorse distress from guilt related to an event or events that occurred during a military deployment. Women and members of diverse ethnic and racial groups will be recruited for this project. Eligibility criteria were designed to recruit a heterogeneous and representative sample of Veterans with guilt and distress related to trauma that occurred on deployment. Eligibility criteria are broad in order to capture the many manifestations of distress related to guilt among Veterans.

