Missing data values will be minimized by intensive training of the assessors in techniques of clarifying answers and checking questionnaires while participants are on-site. When missing values are identified, several approaches to acquire the necessary data will be employed: 1) if at all possible, participants will be rescheduled within 24 hours of completion of tests or interviews; 2) if a participant cannot be rescheduled, an effort will be made to send a tester to the individual's place of residence within the same period; 3) missing data will be examined to assess randomness. We expect missing data to be randomly distributed and will impute appropriate values (see below). Missing data (i.e., loss to follow up) will be tested to determine if it is informative, and the methods developed by [82] and [83] to test for completely random dropouts will be applied. If necessary, the techniques of [84] applicable to generalized

estimating equations models will be used to impute missing values.

We will test whether drop-out is random or systematic by comparing the drop-outs with the study completers on the baseline data. An absence of significant differences would support the random nature of drop-outs. Effect of drop-outs will be minimized by the following steps: First, selected data analysis method allows the inclusion of subjects who drop-out or were terminated early in the study, without relying on data imputation procedures. Therefore, no subjects will be excluded from the analyses due to their study status. Second, effect of any systematic differences between the drop-outs and completers will be explored by including the variable of concern to the model as a covariate.

9.11.2. Primary Outcome Analyses.

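### The Hypothesis 1 analysis set drops randomised participants with no post-baseline evaluation, although the plan promises intent-to-treat tests and its mixed model does not need the exclusion (minor)

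*Combined protocol and SAP*

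**What the plan says.** The general analysis section (9.11.1) makes an unqualified statement: "All hypothesis tests will be intent-to-treat". It adds that nobody will be left out of the analyses because of their study status.

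The Hypothesis 1 text in 9.11.2 narrows this: "Data will be analyzed from all randomized subjects on whom we have a baseline assessment and at least one post-baseline evaluation". Hypothesis 2 follows the same route: "This hypothesis will be analyzed using a method similar to that for testing hypothesis 1".

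Three other statements bear on whether the narrowing is needed:

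- Section 9.3, on timing: "Participants who meet inclusion/exclusion criteria as confirmed by the baseline assessment will be randomized to TrIGR or SCT".
- Section 9.11.2, on the outcome vector: "Responses at baseline through 6 months follow-up will be nested within subjects".
- Section 9.11.2, on the model: "This method allows the inclusion of subjects with missing data or those who were terminated early in the study".

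Section 9.11.1 also offers two safeguards against informative drop-out. One is "We will use pattern-mixture models to assess if there is bias due to drop out or missing data". The other is that systematic differences between drop-outs and completers "will be explored by including the variable of concern to the model as a covariate".

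**The concern.** Eligibility is confirmed at baseline and randomisation follows. Every randomised participant should therefore have a baseline, and only the post-baseline condition can exclude anyone. That condition depends on events after randomisation, so the set is a modified intent-to-treat set, which the plan neither labels nor justifies. Someone who leaves before any post-baseline evaluation is excluded by 9.11.2 and kept by 9.11.1, and the plan does not say which section governs.

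What is at stake is the primary comparison of change in guilt severity. If the people lost early differ in baseline guilt, and differ in another way or number in the other arm, the retained groups no longer start level. The change contrast then carries part of that imbalance. Keeping the baseline-only participants in the likelihood removes this bias under missing at random.

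**Working it through.** **The plan's own figure.** The only stated number nearby is the power for Hypothesis 1 (at least 90% with 150 participants). Whether it can be reproduced depends on choices the plan does not give. For a linear slope, compound symmetry, equally spaced visits and 20% attrition spread evenly over the three post-baseline visits:

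- with a common baseline mean, power is 89.4%, 93.0% and 99.8% at correlations (rho) 0.2, 0.5 and 0.8;
- with separate baseline means, it is 66.5%, 84.8% and 99.7%.

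The present point does not rest on this figure. Restoring the baseline-only participants (10 of 150 under that even spread) adds at most 1.3 percentage points in any even-spread variant tried. If all 30 losses were baseline-only, the gain in the linear, compound-symmetry, separate-baseline case is at most 66.0 − 62.6 = 3.4 points. The issue is bias, not power.

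**Inputs from the documents.** Section 9.1 and the allocation in 9.5.2 give 150 participants, 1:1, so 75 per arm. The power section gives an effect of 0.5 SD at the last time point and rho of 0.2, 0.5 and 0.8. Section 9.5.4 gives up to 20% lost by 6 months. That figure is cumulative, so the baseline-only group is a subset of it, and its size is not given.

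**Assumed inputs.** Loss before any post-baseline score affects 5–15% of one arm only (about 4–11 of 75). The odds of loss double per SD of baseline guilt, and baseline is standard normal.

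**Step 1: shift in the retained baseline mean**, by numerical integration of the logistic loss model:

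| Loss in the arm | Shift (SD) |
|---|---|
| 2% | −0.0137 |
| 5% | −0.0338 |
| 10% | −0.0662 |
| 15% | −0.0978 |

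**Step 2: bias in the change contrast.** Let beta = rho × (follow-up SD / baseline SD), the slope of the final score on baseline. Then bias = (1 − beta) × |shift|. If the loss is in TrIGR, a positive value shrinks the apparent benefit.

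| SD ratio | rho | beta | Bias at 5% | Bias at 15% |
|---|---|---|---|---|
| 1 | 0.2 | 0.20 | 0.8 × 0.0338 = 0.027 | 0.8 × 0.0978 = 0.078 |
| 1 | 0.5 | 0.50 | 0.017 | 0.049 |
| 1 | 0.8 | 0.80 | 0.007 | 0.020 |
| 1.5 (assumed) | 0.2 | 0.30 | 0.024 | 0.069 |
| 1.5 (assumed) | 0.5 | 0.75 | 0.008 | 0.024 |
| 1.5 (assumed) | 0.8 | 1.20 | −0.007 | −0.020 |

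Bias is in baseline-SD units. At an SD ratio of 1.25 and rho 0.8, beta is 1 and the bias is zero. For scale, the standard error of the change contrast at rho 0.5 with no attrition is √(2 × 2(1 − 0.5)/75) = 0.163. The equal-SD bias at rho 0.5 is therefore 0.10–0.30 of a standard error.

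**Step 3: variations.** Eligibility requires high guilt, which restricts the baseline range. With an assumed cut at the mean of an underlying normal, re-standardised, the shifts are −0.044 (5%) and −0.117 (15%). With equal SDs the bias then runs from 0.2 × 0.044 = 0.009 to 0.8 × 0.117 = 0.094. Such restriction may also raise the SD ratio, which lowers the bias while beta stays below 1.

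**Step 4: simulation.** 1.5 million per arm, true 6-month effect −0.50, 15% loss in TrIGR only, except where the first column says otherwise:

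| Set | rho 0.2 | rho 0.5 | rho 0.8 |
|---|---|---|---|
| 9.11.2 set, equal SDs | −0.423 | −0.451 | −0.480 |
| All randomised, saturated arm-by-time, baseline as response | −0.501 | −0.500 | −0.500 |
| 9.11.2 set, same loss in both arms | −0.503 | −0.501 | −0.501 |

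At SD ratio 1.5 and rho 0.8 the 9.11.2 set gives −0.519 and all randomised gives −0.500, confirming the sign reversal.

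**Step 5: does the covariate safeguard repair it?** In complete data a main-effect covariate moves all of a person's visits equally and cancels from change. With baseline guilt added as a main effect to the 9.11.2 set (400,000 per arm), the estimates are −0.424, −0.454 and −0.483, identical with and without it. Only a baseline-by-time term restores −0.500 at each rho. The plan does not say which form is meant.

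**The case against.** The strongest reply is that little turns on this in practice. The one-arm loss model has no support in the documents, and 9.7.2 reports that drop-out under SCT did not differ from other conditions in a past trial. With 10% loss in one arm and 5% in the other, under the same model, the net shift is 0.0662 − 0.0338 = 0.0324. The bias then falls to 0.026, 0.016 and 0.006 SD at rho 0.2, 0.5 and 0.8. The excluded group may also be nearly empty. Participants complete weekly measures, and 9.3 commits to seeking follow-up data from everyone. Section 9.11.2 does not define what counts as a post-baseline evaluation, and the contents of Table 3 could not be read in the text available here. If weekly forms count and an assumed 2% of one arm is excluded, the bias is 0.003–0.011 SD. Finally, 9.11.2 states its set openly, and 9.11.1 offers pattern-mixture estimates averaged over missing-data patterns, with imputation if necessary.

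All of this bears on size, and it is why the point is minor. It does not reconcile the two sections. None of the safeguards is stated to bring the excluded people back. The 9.11.1 promise that study status will not lead to exclusion suggests the authors wanted them included. The undefined term is a further reason to rewrite the sentence.

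**Conclusion.** The concern holds, as a minor one. The Hypothesis 1 set contradicts the intent-to-treat commitment, selects only on events after randomisation, and serves no purpose in a model that has baseline as a response. That conclusion rests on the text and is firm.

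The size is uncertain and probably small: about 0.01–0.08 SD under the main one-arm assumption with equal SDs, up to 0.094 with a restricted baseline, and zero if loss works alike in both arms. The direction is conditional too. Loss of high-guilt people from TrIGR understates the effect only while beta is below 1.

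**What to change.** Replace the sentence in 9.11.2 with: *The analysis set for Hypotheses 1 and 2 is all randomised participants, analysed by assigned arm; participants with only a baseline score are retained, with baseline as a response in the mixed model.* The saturated treatment-by-time model stays as it is.

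Report by arm the number with no post-baseline score, and say whether weekly forms count towards it. Keep the present set as a sensitivity analysis.

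This wording covers Hypotheses 1 and 2 only, and no change is proposed for Hypothesis 3. Because Hypothesis 3 and the exploratory analyses borrow the same model, a clause saying which set they use would avoid a new ambiguity.

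The cost is one sentence replaced, one count by arm and one extra model run, with no new data collection.
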